ATC	Anatomical Therapeutic Chemical
AUC	Area Under the Curve
BFC	Best Fit Circle
BFCr	Best Fit Circle Radius
BFCi	Best Fit Circle Irregularity
CDVA	Corrected Distance Visual Acuity
CEIm	Ethics Committee of Drugs and Medical Devices
CRF	Case Report Form
DCIVA	Distance Corrected Intermediate Visual Acuity
DCNVA	Distance Corrected Near Visual Acuity
FAUC	Far Area Under the Curve
GCP	Good Clinical Practices
IAUC	Intermediate Area Under the Curve
ICH	International Council for Harmonisation
IOL	Intraocular Lens
IOP	Intraocular Pressure
LDI	Light Distortion Index
MIOL	Multifocal Intraocular Lens
MPMAV	Maximum Positive Maximum Visual Acuity
MTF	Modulation Transfer Function
NAUC	Near Area Under the Curve
NdYAG	Neodymium YAG laser for Posterior Capsulotomy
PCO	Posterior Capsular Opacification
SAE	Serious Adverse Event
TAUC	Total Area Under the Curve
UDVA	Uncorrected Distance Visual Acuity
UIVA	Uncorrected Intermediate Visual Acuity
UNVA	Uncorrected Near Visual Acuity
VA	Visual Acuity

1 SYNOPSIS

Name of Sponsor: Qvision, Ophthalmology Department, Vithas Virgen del Mar Hospital, [name]	
Name of Finished Product: AT LISA 839MP	
Title of Study: Long-term visual performance and patient reported outcomes with a trifocal intraocular lens	
Principal Investigator: [name]	
Study centre(s): Qvision, Ophthalmology Department, Vithas Virgen del Mar Hospital, [name]	
Studied period (years): 15-9-2020 to 27-11-2020	Phase of development: Post-market
Objectives: The main aims of this study were to evaluate the patient reported outcomes (PROs), safety and efficacy, after 6-year (66 - 78 months) from the binocular implantation of the 839MP. A secondary aim was to evaluate new metrics such as contrast sensitivity defocus curves and light distortion analysis.	
Methodology: Retrospective cross-sectional study with two stages: 
 • Phone call interview: 
First stage included patient reported outcomes of visual function, spectacle independence and satisfaction through questionnaires conducted by a phone call in all the patients implanted in our center with AT LISA 839MP from March 2014 to June 2015 (n=92) which accomplished inclusion / exclusion criteria and were able to be contacted by phone (n=62).
 
The incidence of Nd-YAG capsulotomy was retrospectively evaluated through the revision of the medical history, in patients for which capsulotomy was conducted in our center, or a question, for those treated in another center.
 
 • Study visit: 
Second stage included the consecutive invitation of these phone interviewed patients to a visit in our center for a long-term visual performance assessment up to accomplish the required sample size (n=37).
 
Corrected and uncorrected monocular visual acuities were the primary end-points for testing non-inferiority hypothesis in comparison to 12-month follow-up mean results reported in the literature. Secondary variables of assessment were contrast sensitivity defocus curve and light distortion analysis.
	

Number of patients (planned and analyzed):
92 for PROs planned and 62 analyzed
37 for visual performance planned and analyzed

Inclusion Criteria:

- Phone call interview:
 - Patients of either sex, 45 years of age or older at the time of surgery and less than 80 years of age at the time of the phone call.
 - Patients implanted bilaterally with the AT LISA 839MP MIOL in the capsular bag.
 - No surgical complications reported in the clinical history that could affect postoperative visual acuity: damage to the capsular bag, intraocular hemorrhage, etc.
 - Operated between 66 months from the first implanted eye and up to 78 months from the surgery of the second eye
 - Patient able to hear, understand and give express consent orally.
- Study visit:
 - To have participated in the first stage of the study corresponding to the phone call interview.
 - Irregular astigmatism in either eye measured with corneal tomography (total high-order corneal aberrations at 4 mm < 0.5 μ m).
 - Patient able to read, understand and provide a written informed consent form.
 - Sufficient availability, willingness, skills, and cognitive awareness to comply with follow-up/study procedures and study visits.

Exclusion Criteria:

- Phone call interview:
 - Any eye disease documented in the patient's clinical history that may potentially cause a loss of visual acuity or diplopia: Active or recurrent pathology of the anterior segment (chronic uveitis, iritis, iridocyclitis, rubeosis iridis, uncontrolled glaucoma, etc.), retinal or optic nerve pathologies such as diabetic retinopathy, macular degeneration, etc.
 - Eye surgery (including laser refractive surgery) performed before or after the operation with the intraocular lens.
- Study Visit:
 - PCO ≥ 2 according to surgeon criteria that produces a loss of CDVA ≥ 0.2 logMAR
 - Any eye disorder that can potentially cause a loss of visual acuity or diplopia: Active or recurrent pathology of the anterior segment (chronic uveitis, iritis, iridocyclitis, rubeosis iridis, uncontrolled glaucoma, etc.), retinal or optic nerve pathologies such as diabetic retinopathy, macular degeneration, etc.
 - Eye surgery (including laser refractive surgery) performed before or after the operation with the intraocular lens.
 - Use of systemic or ocular medications that may affect vision in the last 6 months.
 - Subjects who participate in any clinical trial or research with drugs or medical devices within 30 days prior to entry into this research and/or during the period of participation in this research.

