5.6.1 Hypothesis and sample size calculation

5.6.1.1 Main hypothesis (non-inferiority)

The primary objective was to assess long-term efficacy by measuring monocular visual acuity with and without correction at distance (CDVA and UDVA), intermediate (DCIVA and UIVA) and near (DCNVA and UNVA). The mean monocular visual acuity and the standard deviations taken as reference were obtained from previous literature.¹⁵ Visual acuity was measured on a logMAR scale so that the smaller the variable, the higher the visual acuity.

A contrast of non-inferiority hypotheses with unilateral significance was carried out, rejection of null hypothesis means that non-inferiority was accomplished:

$$H_0 = \mu_a \geq \delta + \mu_b$$

$$H_A = \mu_a < \delta + \mu_b$$

H_0 = Visual acuity at 6 years was higher or equal (poorer) than at 12 months plus a margin δ

H_A = Visual acuity at 6 years was lower (better) than at 12 months plus a margin δ

μ_a = Mean monocular visual acuity obtained after 6 years of follow-up

μ_b = Mean monocular visual acuity reported in a previous clinical study with 12 months of follow-up.¹⁵

δ = 0.1 logMAR or 0.02 logMAR

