5.6.1.2 Study power

The statistical test planned in the protocol for testing the hypothesis was the one-sided one-sample t-test but the one-sided one-sample Wilcoxon Signed test was finally used due to non-normal distribution of the variables. The margin (δ) selected in the protocol was 0.1 logMAR but the hypothesis was finally also confirmed with a margin of 0.02 logMAR. The software G-Power 3.9.1.2 (Universität Düsseldorf) for an alpha level of 0.05 was used to calculate the power considering the standard deviation obtained in our study.

Table 1. Sample size confirmation

Variables	μ_a	μ_b	Power $\delta = 0.1$	Power $\delta = 0.02$
UDVA	0.06 ± 0.12 0.1 [0.1]	0.03 ± 0.13 0 [-]	0.96	0.12
CDVA	-0.05 ± 0.07 -0.1 [0.1]	0.01 ± 0.11 0 [-]	1	0.99
UIVA	0.07 ± 0.09 0.0 [0.1]	0.12 ± 0.13 0.1 [-]	1	0.99
DCIVA	0.08 ± 0.09 0.1 [0.1]	0.11 ± 0.12 0.1 [-]	1	0.94
UNVA	0.08 ± 0.10 0.1 [0.1]	0.27 ± 0.15 0.2 [-]	1	1
DCNVA	0.05 ± 0.06 0 [0.1]	0.25 ± 0.14 0.2 [-]	1	1

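### Section 5.6.1.2 says non-inferiority was confirmed at 0.02 logMAR, but Table 1 puts UDVA, one of the six primary acuities, outside that margin

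*Combined protocol and SAP*

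**What the plan says.** The Synopsis (Methodology) states that "Corrected and uncorrected monocular visual acuities were the primary end-points for testing non-inferiority hypothesis", judged against 12-month means from the literature. Section 5.6.1.1 names six: CDVA, UDVA, DCIVA, UIVA, DCNVA and UNVA. It writes one generic pair of hypotheses, states that "rejection of null hypothesis means that non-inferiority was accomplished", and gives the margin as "δ = 0.1 logMAR or 0.02 logMAR".

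Section 5.6.1.2 explains that 0.1 was the margin chosen in the protocol and adds that "the hypothesis was finally also confirmed with a margin of 0.02 logMAR". It also says that "the one-sided one-sample Wilcoxon Signed test was finally used due to non-normal distribution of the variables". An alpha of 0.05 appears once, for the power calculation. For the tests themselves, section 5.6.1.1 says only that they were one-sided.

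Sections 5.6.1 and 5.6.2 do not say whether all six tests, any one, or an ordered sequence must reject before non-inferiority is claimed overall.

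**The concern.** Six primary tests are summarised by one statement about a single hypothesis. The rule in section 5.6.1.1 works for one test at a time; nothing carries it from six results to one conclusion. At the 0.02 margin the endpoints do not agree, so the missing rule matters. A reader who takes the 0.02 sentence at face value will believe that every primary acuity at six years was shown to be within 0.02 logMAR of the 12-month reference. For UDVA the table beside that sentence shows otherwise.

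**Working it through.** **Inputs.** From Table 1: the 6-year mean and SD (μa, SD), and the 12-month reference mean (μb), treated as fixed. From the Synopsis: n = 37. The margins are 0.1 and 0.02, and alpha is one-sided 0.05.

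**Step 1: reproduce Table 1.** The effect size is (μb + δ − μa)/SD. One-sided noncentral-t power with the Wilcoxon efficiency factor 3/π (effective n = 37 × 3/π) gives:

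- UDVA at 0.1: 0.960 (printed 0.96)
- DCIVA at 0.02: 0.944 (printed 0.94)
- UIVA at 0.02: 0.998 (printed 0.99)

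Using 74 eyes instead gives 0.9996 for UDVA at 0.1, which does not match, so 37 is the right n.

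For UDVA at 0.02 the effect is (0.05 − 0.06)/0.12 = −0.083, which is negative. The printed 0.12 is reproduced (0.123) only if the sign is dropped. In the direction of the alternative hypothesis the power is about 0.02.

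**Step 2: approximate test for each endpoint.** t = (μa − μb − δ)/(SD/√37), 36 degrees of freedom, lower tail.

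| Endpoint | μa (SD) | μb | μa − μb | t, δ = 0.1 | p | t, δ = 0.02 | p |
|---|---|---|---|---|---|---|---|
| UDVA | 0.06 (0.12) | 0.03 | +0.03 | −3.55 | 0.00055 | +0.51 | 0.69 |
| CDVA | −0.05 (0.07) | 0.01 | −0.06 | −13.90 | <0.0001 | −6.95 | <0.0001 |
| UIVA | 0.07 (0.09) | 0.12 | −0.05 | −10.14 | <0.0001 | −4.73 | <0.0001 |
| DCIVA | 0.08 (0.09) | 0.11 | −0.03 | −8.79 | <0.0001 | −3.38 | 0.0009 |
| UNVA | 0.08 (0.10) | 0.27 | −0.19 | −17.64 | <0.0001 | −12.77 | <0.0001 |
| DCNVA | 0.05 (0.06) | 0.25 | −0.20 | −30.41 | <0.0001 | −22.30 | <0.0001 |

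For UDVA the standard error is 0.12/√37 = 0.0197. The upper one-sided 95% bound of the difference is 0.03 + 1.688 × 0.0197 = 0.063, which is above 0.02 and below 0.1.

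**Step 3: rounding.** Within the rounding of the printed means, the UDVA difference lies between 0.0201 and 0.0399, and p between 0.50 and 0.85. Rounding cannot bring it inside 0.02.

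**Step 4: medians.** The UDVA median is 0.1 at six years and 0 in the reference. At δ = 0.02 the limit is 0.02 on medians, or 0.05 on means, and 0.1 exceeds both. At δ = 0.1 the median-based limit is 0 + 0.1 = 0.1, so the observed median sits exactly on it. The t-test against 0.10 gives t = (0.06 − 0.10)/0.0197 = −2.03, p = 0.025, much weaker than the 0.00055 obtained against 0.13.

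**The case against.** **The figures come from the wrong test.** The plan used a one-sample Wilcoxon test, and no Wilcoxon p-values are printed. This stands as a limit on the exact p-values. It does not rescue the 0.02 statement, because both the mean and the median of UDVA are beyond the limit. Simulated samples on a 0.1 logMAR grid (an assumption), matched to the printed mean, SD, median and interquartile range, came nowhere near rejecting.

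It does limit any reassurance about the 0.1 margin. The Synopsis and section 5.6.1.1 refer to reference means, while section 5.6.2 speaks of median differences. In the same simulations the Wilcoxon p for UDVA against 0.10 ran from about 0.004 to 0.09, typically 0.026; against 0.13 it stayed below about 0.01. The result at 0.1 therefore depends on which reference value was used.

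**A reader might infer a familywise error of up to 26%.** The arithmetic is 1 − 0.95⁶ = 0.265 for independent tests, about 18% at an assumed correlation of 0.5 and 10% at 0.9. These figures apply only if any one rejection is enough, and the documents never say that. An all-six reading fits the text at least as well and needs no alpha adjustment. Even 0.05 per test is inferred from the power calculation. Taken alone, the missing rule is a missing detail.

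**A reader might also infer that the UDVA result was concealed.** It was not: Table 1 prints the UDVA means and the low power of 0.12 next to the sentence. The fault is an inaccurate summary beside visible contrary data.

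**Conclusion.** The concern holds in a limited form. The statement that the hypothesis was confirmed at 0.02 is wrong as written, because Table 1 supports it for at most five of the six primary acuities and not for UDVA (difference 0.03, upper bound 0.063, approximate p = 0.69). The 0.02 margin was also not the one selected in the protocol, although section 5.6.1.1 lists it alongside 0.1 as if the two had equal standing.

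The missing rule across endpoints is secondary. It is what allowed a five-of-six result to be written as a single success. No inflated error rate is shown.

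At the planned 0.1 margin all six pass on Table 1 means and t-tests (largest p 0.00055, UDVA). That rests on the mean-based limit and on a t approximation to non-normal data, so it is provisional until the Wilcoxon results are given with their reference value.

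**What to change.** 1. In section 5.6.1.2, replace the 0.02 sentence. Say that at 0.02 logMAR, a post hoc margin not selected in the protocol, Table 1 supports non-inferiority for five of six acuities and not for UDVA.
2. In section 5.6.1.1, keep 0.1 as the only confirmatory margin.
3. Add there, dated as a clarification made after the data were known, that an overall non-inferiority claim requires all six one-sided tests to reject at 0.05. No alpha adjustment is needed. If any test does not reject, results are reported endpoint by endpoint. The rule must not be presented as prespecified.
4. State the reference value (mean or median) used in the Wilcoxon tests, and report the six Wilcoxon p-values at 0.1.
5. Correct the UDVA power at 0.02 in Table 1, or note that the effect is in the unfavourable direction.

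The cost is a few sentences and six p-values from data already in hand. The overall 0.02 claim is lost. The 0.1 conclusion stands if the Wilcoxon results confirm it.

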3 INTRODUCTION

The implantation of multifocal intraocular lens (MIOL) has become a settled method for cataract treatment mainly due to the high rate patient satisfaction ranging from 81.4% to 96.3%.¹ Although there is a lot of clinical evidence that demonstrates the safety and efficacy achieved with MIOLs in the short term period, which explain the high satisfaction rates,²⁻¹⁰ long-term results still remain poorly investigated. First long-term study with 8-year follow-up was reported for 3M diffractive MIOL which was made of a poly(methyl methacrylate) material, nowadays outdated technology.¹¹ Most recent bifocal optic and material such as the provided by the Acrysof ReSTOR (SN60D3, Alcon) has also long-term results available.¹² Yoshino et al.¹² reported 5-year follow-up with no differences in distance and near visual acuities in comparison to 1-year, contrast sensitivity function in the normal range and 14.3% of neodymium-YAG (Nd-YAG) capsulotomy rates performed in a mean time of 44.64 months. However, as far as we know, no more long-term studies for bifocal MIOLs have been published, probably because of the decrease on interest by the replace for the current more popular trifocal intraocular lenses (IOLs).

The AT LISA tri 839MP (henceforth 839MP, Carl Zeiss Meditec AG, Germany) was together with the FineVision (Physiol S.A., Liege, Belgium) the first trifocal MIOLs which received the CE mark in 2012 and 2010, respectively.¹³ Safety and efficacy for 839MP has been widely reported for short term follow-up periods (1 to 6 month follow-up).²⁻¹⁰ Long-term studies with 839MP are commonly referred to those which involve 1 or 2 year follow-up period¹⁴⁻¹⁸ and as far as we know there is only one retrospective study for a higher period of 3-4 years follow-up which only covers Nd-YAG rates.¹⁹ 839MP remains one of the most popular and implanted MIOLs and therefore the results for longer periods of time can be considered of great interest.

4 STUDY OBJECTIVES

The main aims of this study were to evaluate the patient reported outcomes (PROs), safety and efficacy, after 6-year from the binocular implantation of the 839MP. A secondary aim was to evaluate new metrics such as contrast sensitivity defocus curves and light distortion analysis.

5 METHODS

5.1 Ethics

5.1.1 Ethics Committee for investigation with medicinal products (CEIm)

The protocol, informed consent forms, recruitment materials and all participant materials were submitted to the CEIm for review and approval. The study was approved on 29/07/2020 by the local ethics committee (Hospital Universitario de Torrecárdenas, [name]) before participant enrollment. No amendments of the protocol were conducted.

5.1.2 Ethical conduct of the study

The study was conducted in accordance with the ethical principles that have their origins in the Declaration of Helsinki and the standards of Good Clinical Practice, as well as European legislation Regulation 536/2014, National Law 14/2007 on Biomedical Research and Autonomous Decree 439/2010, Law on Patient Autonomy 41/2020 and Law 3/2018 on Data Protection and Digital Rights Guarantee.

5.1.3 Patient information and consent

Two informed consents were given depending on the phase of the study:

- For the first stage, the consent was obtained by telephone, the patient was informed about the study and expressed verbal consent for using his/her pseudonymized data in the research. The participant gave the consent orally, the investigator signed the consent form and the date of consent was notified in the patient's medical record. The consent form was stored with the source documents of the study to be provided to the patient to obtain his/her written signature and to receive a copy at the time of his/her visit to the center. This procedure was carried out according to version 12 of June 29, 2020 of the Spanish Agency of Medicines and Healthcare Products' document of instructions for conducting clinical trials in Spain in reference to obtaining consent in COVID-19 studies.
- For the second stage at the clinical center, participants were provided with a patient information sheet with the risks and possible benefits of participating in the study as well

as the sheet corresponding to the first part of the study. The participant signed both informed consent documents before any evaluation or procedure related to study visit. A copy was given to the participants.

The rights and well-being of participants were protected by emphasizing that the quality of their clinical care was not adversely affected if they refused to participate in the study.

[figure not shown]
5.2 Investigational Plan

5.2.1 Investigational Product

The AT Lisa Tri 839MP is a trifocal intraocular lens with a 6.0 mm biconvex optic (360° posterior square edges) and overall diameter of 11.0 mm including the non-angulated plate haptic. The material consists of a hydrophilic acrylate with a water content of 25% with hydrophobic surface and blocks ultraviolet light according to manufacturer description. The optic structure is diffractive with additions at the IOL plane of +3.33 D for near focus and +1.66 D for intermediate focus and a posterior aspheric surface lead to an induction of negative spherical aberration of $-0.18 \mu\text{m}$.^{13,20}

5.2.2 Overall Study Design

The study design was retrospective and cross-sectional. The study consisted of two stages, the first one with a phone call interview for collecting the PROs, and a second stage with the consecutive invitation of these patients to a visit at our center to measure the visual performance up to achieve the required sample size. Each stage with some inclusion and exclusion criteria detailed below. The diagram in Figure 1 summarizes the study stages.

^aStudy Visit delayed until the resolution of the subsequent capsular opacification by Nd:YAG capsulotomy

Figure 1. Study design summary

5.3 Selection of study sample

5.3.1 Phone call interview

5.3.1.1 Inclusion criteria

- Patients of either sex, 45 years of age or older at the time of surgery and less than 80 years of age at the time of the phone call.
- Patients implanted bilaterally with the AT LISA 839MP MIOL in the capsular bag.

-
- No surgical complications reported in the clinical history that could affect postoperative visual acuity: damage to the capsular bag, intraocular hemorrhage, etc.
 - Operated between 66 months from the first implanted eye and up to 78 months from the surgery of the second eye.
 - Patient able to hear, understand and give express consent orally.

5.3.1.2 Exclusion criteria

- Any eye disease documented in the patient's clinical history that may potentially cause a loss of visual acuity or diplopia: Active or recurrent pathology of the anterior segment (chronic uveitis, iritis, iridocyclitis, rubeosis iridis, uncontrolled glaucoma, etc.), retinal or optic nerve pathologies such as diabetic retinopathy, macular degeneration, etc.
- Eye surgery (including laser refractive surgery) performed before or after the operation with the intraocular lens.

5.3.2 **Study visit**

5.3.2.1 Inclusion criteria

- To have participated in the first stage of the study corresponding to the Phone Call Interview.
- Irregular astigmatism in either eye measured with corneal tomography (total high-order corneal aberrations at 4 mm $< 0.5 \mu\text{m}$).
- Patient able to read, understand and provide a written informed consent form.
- Sufficient availability, willingness, skills, and cognitive awareness to comply with follow-up/study procedures and study visits.

5.3.2.2 Exclusion criteria

- PCO ≥ 2 according to surgeon criteria that produces a loss of CDVA $\geq 0.2 \log\text{MAR}$
- Any eye disorder that can potentially cause a loss of visual acuity or diplopia: Active or recurrent pathology of the anterior segment (chronic uveitis, iritis, iridocyclitis, rubeosis iridis, uncontrolled glaucoma, etc.), retinal or optic nerve pathologies such as diabetic retinopathy, macular degeneration, etc.

-
- Eye surgery (including laser refractive surgery) performed before or after the operation with the intraocular lens.
 - Use of systemic or ocular medications that may affect vision in the last 6 months.
 - Subjects who participate in any clinical trial or research with drugs or medical devices within 30 days prior to entry into this research and/or during the period of participation in this research.

5.4 Safety Evaluation

5.4.1 Definition of adverse events

An adverse event (AE) was defined as an adverse or unfavorable medical occurrence in a subject, including any abnormal sign (e.g., an abnormal physical examination), symptom, or disease, temporally associated with the subject's participation in the research, whether or not it is considered related to the subject's participation in the research. Some adverse events could happen during the 6 years period between the surgery date and the study visit, some of these adverse events were identified and reported even these could be part from the Exclusion Criteria. In this case, those were reported as a recruitment failure together with the adverse event reason. A list of possible adverse events anticipated can be found in ISO-11979-7:2018.²¹

